# 2.7.2 Deaths

Patient deaths will be summarized as all-cause mortality and by cause of death at 30 days, 90 days and through 12-months. A patient listing of all deaths will also be provided.

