	
9. Quality of life (QOL) as measured by the Pulmonary Embolism Quality of Life (PEmb-QOL) and EuroQol five dimension five level questionnaire (EQ-5D-5L) at 3 month and 12 month post-hospitalization follow-up visits
 
10. IVC filter placement (measured by number of occurrences)

	
RETROSPECTIVE
 
Data collection is expected to occur over a 6 month period at each site

Trial Duration	
PROSPECTIVE
 
Enrollment will take place over approximately a 24 month period. For each subject, their participation in the registry lasts 12 months.

Trial Design	
A multi-center retrospective and prospective registry of the APT treatment of patients (pts) with submassive (Intermediate-High Risk) and massive (High Risk) PE. The retrospective portion of the registry will consist of consecutive patients treated with APT between January 1, 2014 and one year prior to date of site activation. The prospective portion of the registry will collect data for pts diagnosed and risk-stratified and treated with APT procedure. Pts will be followed for 12 months.

	
Intermediate-High Risk PE will be defined by evidence of RV dysfunction (<math>RV/LV \geq 1.0</math>), hemodynamic stability (normal systemic arterial blood pressure <math>>90</math> mmHg), and troponin elevation.
 
High Risk PE will be defined with hemodynamic instability (normal systemic arterial blood pressure <math><90</math> mm Hg and/or use of vasopressors)

Number of Patients	
RETROSPECTIVE
 
Up to 1000 evaluable cases

	
PROSPECTIVE
 
Up to 550 consented patients to yield 500 evaluable patients

Number & Location of Sites	
Up to 100 sites geographically distributed throughout North America, Europe, and Asia

Eligibility Criteria	
RETROSPECTIVE
 
Inclusion Criteria
 

1. Treated with APT procedure between January 1, 2014 and one year prior to date of site activation

2. <math>RV/LV \geq 1.0</math> from diagnostic CTA or echocardiogram

3. PE symptom duration <math>\leq 14</math> days

	
4. Troponin elevation
 
Exclusion Criteria
 
5. Enrollment into the OPTALYSE PE study

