### 6.2.1 Inclusion Criteria

---

Retrospective cases must meet all of the following inclusion criteria:

1. Treated with APT procedure between January 1, 2014 and one year prior to date of site activation
2. RV/LV  $\geq 1.0$  from diagnostic CTA or echocardiogram
3. PE symptom duration  $\leq 14$  days
4. Troponin elevation

Prospective subjects must meet all of the following inclusion criteria:

5. Male or female  $> 18$  years of age and  $\leq 80$  years of age
6. RV/LV  $\geq 1.0$  from diagnostic CTA or echocardiogram
7. PE symptom duration  $\leq 14$  days
8. Troponin elevation
9. Signed informed consent obtained from subject or legally authorized representative
10. Investigator has selected EKOS to treat patient with massive or submassive PE

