### **13.10 Interim Analysis**

Periodic statistical summaries will be prepared annually.

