# 2.2 **Populations**

Safety Population (SP) - The SP will be defined as all patients who receive the APT procedure. Safety and effectiveness summaries will be reported for the SP.

Efficacy Population (EP) - The EP will be defined as all patients who meet eligibility criteria. An additional effectiveness summary will be reported for the EP.

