# 2.7 Safety analyses

Safety analyses will be performed for the SP during hospitalization and through the 12-month follow-up period. In addition to the analyses described below, safety analyses will also be summarized by the subgroups described in section 2.2.1.

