#### 2.8 Interim analysis

Periodic statistical summaries will be prepared semi-annually, to include the following at a minimum:

- Disposition summaries as per section 2.3.1
- Study treatment summaries as per section 2.4.1
- Safety summaries as per section 2.7.1 (2.7.1.3 a, d, i-m) and 2.7.2

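### Twelve-month death, major bleeding and VTE default to simple percentages with no rule for incomplete follow-up, which matters mainly for prospective figures at the periodic summaries

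*SAP*

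**What the plan says.** **Population and horizon.** SAP 2.7: "Safety analyses will be performed for the SP during hospitalization and through the 12-month follow-up period". SAP 2.2: "The SP will be defined as all patients who receive the APT procedure". No minimum follow-up is required.

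**Estimator.** SAP 2.1 summarizes categorical data by counts and percentages. SAP 2.7.1.2 does the same for adverse events, and SAP 2.7.1.3 applies this at 30 and 365 days, including major bleeding and VTE. On deaths, SAP 2.7.2 says only: "Patient deaths will be summarized as all-cause mortality and by cause of death at 30 days, 90 days and through 12-months". Neither document mentions Kaplan-Meier, cumulative incidence, censoring, person-time or a denominator based on follow-up.

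**Timing.** On prospective patients, the Protocol synopsis says "Enrollment will take place over approximately a 24 month period", with 12 months of participation each. Retrospective cases must have been "Treated with APT procedure between January 1, 2014 and one year prior to date of site activation", so a full year has elapsed for all of them, but Protocol 8.4 collects their long-term data only where available. Protocol 6.4 foresees withdrawal and loss.

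**Periodic summaries.** SAP 2.8: "Periodic statistical summaries will be prepared semi-annually", with a minimum content that includes "Safety summaries as per section 2.7.1 (2.7.1.3 a, d, i-m) and 2.7.2". That covers major bleeding, VTE and deaths. Protocol 13.10 differs: "Periodic statistical summaries will be prepared annually".

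**Precision.** Protocol 13.1 promises 95% confidence intervals for each outcome measure. SAP 2.7 mentions none.

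**The concern.** If all treated patients form the denominator, someone followed for four months without an event counts as event-free at twelve. Observed events over all treated patients cannot exceed true 12-month events over the same number, so on that denominator the error can only be downward.

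The second objective is to describe long-term outcomes by APT regimen, and safety is to be shown by dose category and by portion of the registry. Groups with equal true risk will show different percentages if their follow-up completeness differs. The first objective expects practice to shift over time, so regimens used more recently would also have shorter follow-up at a periodic summary. SAP 2.3.1 tabulates follow-up completeness and duration on study, but nothing links these to the event percentages.

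**Working it through.** The plan states no 12-month risk, event count or loss rate, so there is no figure of its own to reproduce. Everything below is illustration.

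**Inputs from the documents:** enrollment about 24 months; 12 months of follow-up each; 550 consented to yield 500 evaluable (1 − 500/550 = 9.1%, not stated to be attrition).

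**Assumptions:** true 12-month mortality R = 10%; even accrual; a share E of deaths before discharge, E = 1/3 or 2/3.

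**1. Follow-up at a summary T months after the start.** Follow-up is the smaller of 12 months and T minus entry time.

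| T | Share with full 12 months | Mean follow-up (months) |
|---|---|---|
| 12 | 0 | 6 |
| 18 | 1/3 | 8 |
| 24 | 1/2 | 9 |
| 30 | 3/4 | 11.25 |
| 36 | 1 | 12 |

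**2. Expected crude percentage, prospective portion, no loss.**

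- Remaining deaths even over the year: R × [E + (1 − E) × mean follow-up/12]. At T = 24: 10% × (0.333 + 0.667 × 0.75) = 8.3%, or 10% × (0.667 + 0.333 × 0.75) = 9.2%. At T = 12, 18 and 30 the ranges are 6.7–8.3%, 7.8–8.9% and 9.6–9.8%. At T = 36 the figure is 10%.
- Constant hazard at T = 24: half the patients are complete (10%). The other half have follow-up spread over 0–12 months and average 1 − 0.1/(−ln 0.9) = 5.1%. The mean is 7.5%.
- Remaining deaths all within three months, T = 24: the share observed is (3/24) × 0.5 + 21/24 = 0.9375. This gives 10% × (0.333 + 0.667 × 0.9375) = 9.6%, or 9.8% with E = 2/3.

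So month 24 shows 7.5% to 9.8% on timing alone.

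**3. Kaplan-Meier on the same kind of data.** Simulation with 9.1% lost evenly over the year, under constant hazard or half of events in month 1:

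| T | Crude | Kaplan-Meier |
|---|---|---|
| 18 | 6.4–7.9% | 9.9–10.0% |
| 24 | 7.3–8.4% | 10.0–10.1% |
| 36 | 9.5–9.7% | 10.0% |

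**4. Final analysis with loss L.** Crude = R × [E + (1 − E)(1 − L)] for loss at discharge, with 1 − L/2 in place of 1 − L for even loss.

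- L = 9.1%: 9.4–9.8%. Other event timings give 9.1–9.7%. The shortfall is at most 0.6 to 0.9 points. The 95% half-width at n = 500 is 1.96 × √(0.1 × 0.9/500) = 2.6 points, and 1.9 at n = 1000.
- L = 30% (no source in the documents): 8.0–9.5%. A known-status denominator gives crude/(crude + 0.9 × 0.7): 0.08/0.71 = 11.3% up to 0.095/0.725 = 13.1%.

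**5. Prospective against retrospective at month 24, equal true risk.**

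- Retrospective records complete: 8.3/10 = 0.83 to 9.2/10 = 0.92.
- 30% of retrospective cases without status after discharge: retrospective crude is 8.0% (E = 1/3) or 9.0% (E = 2/3), so the ratio is 1.04 or 1.02.

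The direction reverses.

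**6. Non-fatal events.** With 10% mortality, a true incidence of 4.6–4.7% and 30% loss, crude gives 3.2–4.0%, cumulative incidence with death competing 4.6–4.7%, and one minus Kaplan-Meier with deaths censored 5.0%.

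**The case against.** **The denominator for deaths is inferred.** SAP 2.7.2 does not state one. Protocol 13.11 says observed data are summarized without imputation, and counting a patient of unknown status as event-free sits awkwardly with that. The table shells are a separate document and may settle it. This stands in part: a reader might infer that the plan prescribes all-treated percentages for deaths and so must understate risk, but the documents do not go that far. All treated patients remains the natural reading, because SAP 2.7.3 and 2.7.4 say so when an observed-only set is meant, and SAP 2.7 does not repeat the observed-data sentence found in 2.5 and 2.6.

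**The prospective portion need not look safer.** A reader might infer that it must, because only prospective patients are cut off by the calendar. That requires near-complete retrospective records, which Protocol 8.4 does not promise; step 5 shows the reversal. SAP 2.8 also does not say that periodic safety tables are split by subgroup; that follows only from the general sentence in SAP 2.7.

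**The summaries drive no decision.** No test or stopping rule is attached, and disposition is reported alongside. This stands and limits the severity.

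**Kaplan-Meier is not always closer.** This stands too. With 30% loss at discharge and patients who later die half as likely to be lost, E = 1/3 gives Kaplan-Meier 11.3% against crude 9.0%, errors of +1.3 and −1.0 points; E = 2/3 gives 10.7% against 9.5%. If they are 1.5 times as likely to be lost, at discharge or evenly over the year, Kaplan-Meier gives 8.7–9.7% against 7.0–9.3%. Where chart contact depends on illness, non-informative censoring is doubtful.

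**Conclusion.** The gap is real and should be fixed. For 12-month death, major bleeding and VTE the plan defaults to counts and percentages in all treated patients, with no censoring rule, while its own timetable guarantees incomplete prospective follow-up at the periodic summaries.

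The effect is material mainly there: an assumed 10% shows as about 7.5–9.8% at month 24. It is small at the final analysis if loss is near 9%, and below the sampling error. Heavier loss in retrospective records would matter more, but the documents give no rate. Thirty-day figures are little affected.

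Comparisons between portions or dose categories can be distorted in either direction, depending on how complete the retrospective records are. The outcomes are descriptive, so no test is invalidated. All sizes rest on assumed risk, event timing, even accrual and loss.

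**What to change.** - **SAP 2.7.2:** report Kaplan-Meier all-cause mortality at 30, 90 and 365 days with the 95% intervals promised in Protocol 13.1, censored at last known contact or data cut-off, with numbers at risk.
- **SAP 2.7.1.3, major bleeding and VTE at 365 days:** report cumulative incidence with death as a competing event.
- **Crude counts:** keep them, name the denominator, and give the number with known 12-month status. State that non-informative censoring is assumed and that this is doubtful for retrospective records. A sensitivity bound giving censored patients 0.5 and 2 times the observed post-discharge risk is optional.
- **SAP 2.8:** show 12-month prospective figures only by these estimators once patients are at risk near 12 months, or only for patients treated at least 12 months before the cut-off. At month 12 almost no prospective patient has a full year, so no method supports such an estimate. Reconcile the semi-annual and annual frequencies.
- **Pulmonary hypertension:** remove it from the 30-day window in SAP 2.7.1.3, since Protocol 5.3 requires persistence for three months or more, and report it with the number imaged.
- **Dates:** confirm that death and last-contact dates exist for retrospective cases. Protocol 8.4 lists mortality and cause but no date, although the duration on study in SAP 2.3.1 suggests an end date is held.

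**Cost:** SAP wording and standard procedures. For prospective patients, Protocol 6.4 and 10.4 already call for last contact, time of withdrawal and time of death. If the case report form lacks them, two dates must be collected for up to 1000 retrospective cases. Intervals widen: a half-width of 2.9–3.0 against 2.4–2.6 points at month 24 with n = 500.

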#### 2.7.3 Vital Signs

Descriptive summaries for vital sign measurements will be presented by visit in mean, median, standard deviation, minimum and maximum. Baseline, time point value and change from baseline will be presented for each visit and patients having both baseline and corresponding time point will be summarized.

#### 2.7.4 Laboratory tests and Biomarkers

Descriptive summaries for laboratory tests and biomarkers will be presented by visit in mean, median, standard deviation, minimum and maximum. Baseline, time point value and change from baseline will be presented for each visit and patients having both baseline and corresponding time point will be summarized.

#### 2.8 Interim analysis

Periodic statistical summaries will be prepared semi-annually, to include the following at a minimum:

- Disposition summaries as per section 2.3.1
- Study treatment summaries as per section 2.4.1
- Safety summaries as per section 2.7.1 (2.7.1.3 a, d, i-m) and 2.7.2

#### 2.9 Sample size

For retrospective cases, up to 1000 cases will be collected to capture details of PE treatment with EKOS from the time the device was cleared for treatment of PE to the time each site was activated. For prospective, up to 500 patients will be treated to collect data on current EKOS use at up to 100 sites.

# 3 Appendix

#### **3.1** Imputation rules

#### 3.1.1 AE date imputation

The following algorithm should be used to estimate start dates for which only partial information is known:

- Missing day and month
  - If the year is the same as the year of first study treatment, then the day and month of the start date of treatment will be assigned to the missing fields
  - If the year is prior to the year of first study treatment, then December 31 will be assigned to missing fields
  - If the year is after the year of first study treatment, then January 1 will be assigned to the missing fields
- Missing month only
  - Treat day as missing and replace both month and day accordingly to the procedure above
- Missing day only
  - If the month and year are the same as the year and month of first study treatment, then the start date of treatment will b assigned to the missing day
  - If the month and year are before the year and month of first study treatment, then the last day of the month will be assigned to the missing day
  - If the month and year are after the year and month of the first study treatment, then the first day of the month will be assigned to the missing day

If the imputed start date result is after the stop date (and the stop date is complete), the imputed start date will be reset to the stop date.

The following algorithm should be used to estimate stop dates for which only partial information is known:

- Missing year
  - Date left missing
- Missing month
  - Impute "December"
- Missing day
  - Impute last day of that month

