#### 2.7.1.3 Analysis

The following summaries will be provided (within 30 days; within 365 days):

- a. Overall summary of AEs
- b. All AEs by primary SOC and PT
- c. AEs suspected to be related to procedure and/or device by primary SOC and PT
- d. Serious adverse events (SAEs) by primary SOC and PT
- e. SAEs suspected to be related to procedure and/or device by primary SOC and PT
- f. AEs leading to discontinuation by primary SOC and PT
- g. Most frequent AEs (5% or 10%) by primary SOC and PT
- h. Bleeding Events
- i. Major Bleeding Events (within 72 hours; within 30 days; within 365 days)
- j. VTE (DVT and PE)
- k. diagnosis of pulmonary hypertension
- 1. composite measure of recurrent symptomatic PE, PE related death or hemodynamic collapse at 30 days
- m. Death resulting from AEs by primary SOC and PT

In addition, the following summaries will also be provided by subgroups described in section 2.2.1.

- Overall summary of AEs
- All AEs by primary SOC and PT
- SAEs by primary SOC and PT
- Most frequency AEs (5% or 10%) by primary SOC and PT

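### The AE start-date imputation is not confined to the treatment-emergent flag, so some partly dated late events will be counted as early ones in the 72-hour and 30-day summaries

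*SAP*

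**What the plan says.** SAP 3.1.1 gives one algorithm for partial AE start dates:

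- Day and month missing, year equal to the treatment year: "then the day and month of the start date of treatment will be assigned to the missing fields".
- Month missing only: "Treat day as missing and replace both month and day accordingly to the procedure above". A recorded day is discarded, and in the treatment year the event again receives the APT date.
- Day missing only, event in the treatment month: "then the start date of treatment will b assigned to the missing day".
- Day missing, later month: "then the first day of the month will be assigned to the missing day".
- Day and month missing, later year: "then January 1 will be assigned to the missing fields".

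The only correction applies when the imputed start falls after a complete stop date. In that case "the imputed start date will be reset to the stop date", which can only move the start earlier.

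SAP 2.7.1.2 defines treatment-emergent events by onset on or after the first day of APT. SAP 2.7.1.3 reports its AE summaries within 30 and 365 days, and item i adds a shorter window: "Major Bleeding Events (within 72 hours; within 30 days; within 365 days". The SAP gives no separate date rule for these windows, no flag for imputed dates and no sensitivity count.

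Protocol 13.11 says that missing values are not imputed. The SAP repeats this for efficacy (2.5) and additional outcomes (2.6), but not for safety (2.7).

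**The concern.** Moving a partial date to the treatment date is a usual, cautious way to decide whether an event is treatment emergent. It is not a cautious estimate of when the event happened. If the same imputed date is used for time since APT, a bleed that occurred months later and was recorded with the year only becomes a day-0 event.

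Major bleeding is part of outcome measure 5 in protocol 5.3. SAP 2.2.1 and 2.7 call for safety outcomes by dose category and by retrospective versus prospective portion, and SAP 2.8 repeats the major-bleeding summary semi-annually. If partial dates were more common in one portion or dose group, the artefact would look like a difference in early bleeding between them.

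**Working it through.** There is no planned figure to reproduce. The check applies the rules of SAP 3.1.1 to possible onset dates and compares true with imputed time since APT.

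**Inputs.** The rules come from SAP 3.1.1 and the windows (72 hours, 30 days) from SAP 2.7.1.3. Follow-up is 12 months (protocol 5.2, 8.4). The onset distribution is an assumption, so two are shown. Treatment dates are taken as uniform over a 365-day year.

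**Single cases** (non-leap years)

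| APT | True onset | Recorded | True day | Imputed day |
|---|---|---|---|---|
| 10 Feb | 20 Nov, same year | year | 283 | 0 |
| 5 Mar | 28 Apr | month, year | 54 | 27 |
| 30 Mar | 25 Apr | month, year | 26 | 2 |
| 10 Dec | 15 May, next year | year | 156 | 22 |

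**Year only, treatment year.** The imputed offset is always 0, while the true offset can reach 364 days. The share truly within s days is:

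- Constant hazard over 12 months: 2s/365 − (s/365)². For s = 3: 0.0164 − 0.0001 = 0.016. For s = 30: 0.1644 − 0.0068 = 0.158.
- Uniform over the rest of the calendar year: (s/365)(1 + ln(365/s)). For s = 3: 0.00822 × 5.80 = 0.048. For s = 30: 0.0822 × 3.50 = 0.288.

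So about 2-5% truly belong in the 72-hour window and 16-29% in the 30-day window. The rule puts 100% in both.

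**Day missing, treatment month.** The same formulas with a 30-day month and s = 3 give 2(0.1) − 0.01 = 0.19 and 0.1 × (1 + ln 10) = 0.33. So 19-33% truly fall within 72 hours, and the rule counts all of them. The largest possible true offset is 30 days (1st to 31st), so this rule moves no event wrongly into the 30-day window.

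**Day-by-day enumeration.** Every APT date was crossed with every onset from day 0 to day 365, all equally likely, with cut-offs at day 3 and day 30.

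- Year only, treatment year: 97.8% truly fall after day 3 and 83.8% after day 30.
- Day missing, treatment month: 75.8% truly fall after day 3.
- Day missing, any month: the share counted within 72 hours rises from 1.1% to 5.1%. Of these 4.0 points, 3.3 come from the treatment-month rule and 0.8 from the first-of-month rule (rounded). The share within 30 days rises from 8.5% to 12.5%, all from the first-of-month rule.
- No event is moved out of either window.

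**Reach of the later-date rules.** January 1 lies within 30 days of APT only for treatment from 2 December on, and within 3 days only from 29 December on. The first-of-month rule acts mainly on onset in the month after APT. It reaches the 72-hour window only when APT falls in the last three days of a month.

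**Effect on a rate.** Each truly late patient counted as early, with no other early event, adds 1/N: 0.20 points at N = 500, 0.10 at N = 1000, 0.07 at N = 1500.

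**The case against.** The strongest reply is that few major bleeds will have partial dates. Protocol 12.1.6 requires a fatal or critical-site bleed, a haemoglobin fall of 20 g/L or more, or transfusion of two or more units, and such events normally leave dated records. Protocol 12.2 requires bleed-related SAEs to be reported within one working day of awareness in both portions, and protocol 15.11 provides for queries on missing or unclear data. This stands as an argument about size. It does not change what the rule does to the events that remain partly dated.

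The current rule also errs toward overcounting early harm, in a registry that plans no safety hypothesis test, and SAP 2.1 lists all collected and derived data. That stands too. But a reader of the summary tables could not tell imputed early events from observed ones.

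Four stronger readings are tempting, and the documents do not support them:

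- **That every branch inflates every window.** The treatment-month rule cannot inflate the 30-day count, and the treatment-year and treatment-month rules cannot inflate the 365-day count.
- **That early major bleeding is the main safety quantity for comparing regimens.** No primary safety endpoint is named. The 72-hour window appears only in item i, and the explicit subgroup list in SAP 2.7.1.3 omits bleeding, although 2.2.1 and 2.7 are broader.
- **That partial dates come mainly from chart review or phone contacts.** Retrospective follow-up is collected where available (protocol 8.4) and prospective follow-up may be by phone (protocol section 3), so this is plausible. No figure supports it.
- **That the reported 72-hour rate would be materially wrong.** This needs a count of partly dated bleeds that neither document gives.

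**Conclusion.** The point holds in limited form. As written, SAP 3.1.1 dates feed the onset windows, and the resulting error can only run toward early events. Year-only events in the treatment year are affected in both short windows, treatment-month events in the 72-hour window only, and later partial dates mainly in the 30-day window.

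The shares of 2-5%, 16-29% and 19-33% rest on constant or uniform onset and uniform treatment dates. If bleeding clusters soon after APT, more of these events are truly early and the error is smaller. The effect on the reported rates cannot be sized from the documents. For major bleeding it is probably small; partial dates are more plausible for less serious events.

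**What to change.** 1. State in SAP 3.1.1 that the imputed start date is used only for the treatment-emergent flag.
2. For the 72-hour and 30-day summaries, derive the earliest and latest onset consistent with the recorded date parts, the APT date, any complete stop date and any other recorded bound. Hospital discharge is one such bound for an event first reported at follow-up, where available; protocol 8.3 already collects it for retrospective cases.
3. Count an event as inside the window if its latest possible date is inside, and as outside if its earliest possible date is outside. Show the rest as undetermined in a separate row.
4. Report both the lower count (undetermined excluded) and the upper count (undetermined included). Simply dropping undetermined events would bias early bleeding downward, so neither count should stand alone.
5. Reconcile SAP 3.1.1 with protocol 13.11, for example by stating that date imputation for the treatment-emergent flag is an exception.

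The cost is a few lines of SAP text, slightly more programming and one extra table row, with no new data. Retrospective cases with few recorded contacts will have wide bounds, and more of their events will be undetermined. If partial dates prove rare, the row will show that.
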